9.5 Visit 4 (Day 56 ± 2 days)

Participants will attend remotely for Visit 4 assessments with completed study diaries inclusive of the CARIFS, Additional respiratory tract symptoms, and GITI symptoms questionnaires.

Visit 4 assessments include:

- 1. Review compliance by referencing study diaries and participant/caregiver count of study product.
- 2. Review completed study diaries including CARIFS, Additional respiratory tract symptoms, and GITI symptoms questionnaires
- 3. Review concomitant therapies and AEs
- 4. Dispense new study diary
- 5. Participants will be reminded to bring saliva and stool samples for the End of Study visit.

The next visit will be scheduled for Day 84 (\pm 2 days).

9.6 Visit 5 - End of Study (Day 84 ± 2 days)

Participants will return to the clinic for end of study assessments, with unused investigational product, completed study diaries (inclusive of the CARIFs, Additional respiratory tract symptoms, and GITI symptoms questionnaires), and stool and saliva samples.

Visit 5 assessments include:

- 1. Return and review study diary
- 2. Return unused investigational product in the original packaging and remnants and calculate compliance by counting the returned unused investigational product
- 3. Review concomitant therapies and AEs
- 4. Vital sign measurements (BP and HR)
- 5. Weight and height measurements
- 6. Urine pregnancy test for participants that are of childbearing potential
- 7. Collect blood samples for the analysis of:
 - a. Quantibody® Human Immune Response Array
 - b. Immunoglobulins A (IgA), G (IgG), E (IgE) and M (IgM) serum levels
- 8. Collect saliva samples for the analysis of Salivary Ig A Levels
- 9. Collect stool samples for microbiome analysis
- 10. Review completed study diaries including CARIFS, Additional respiratory tract symptoms, and GITI symptoms questionnaires

9.7 Clinical Assessments and Procedures

Calculations or measurements of specific parameters are required, as indicated in the Schedule of Assessments. Instructions for determining these parameters are provided in the following sections.

9.7.1 Height and Weight

Weight measurements will be performed with shoes removed and bladder empty on calibrated scales at all visits.

At least two separate measurements will be taken at each visit. If the two measurements are more than $0.5 \, \text{kg} (1.1 \, \text{lbs})$ apart, a third measurement will be taken. The two closest values will be selected for computation.

Measurement of height will be performed with the participant's shoes removed. The participant's knees will be straightened, and head held upright.

9.7.2 Blood Pressure and Heart Rate

In-office, seated, resting BP assessment:

The participant should be seated comfortably with their back supported and the upper arm bared without restrictive clothing. Feet should be flat on the floor and legs will not be crossed. The participant will rest in this position for at least five minutes prior to the first reading.

At screening:

Seated BP will be checked in both arms to ensure that the arm with the higher BP reading will be used for BP measurements of the study. The arm chosen for use at the initial visit will be documented in the study file and used in all subsequent visits. Participants and/or Caregivers of participants with elevated BP should be queried about the participants usual BP. As per the QI's opinion, a high office BP should be rechecked after the participant is given a glass of water and is rested for 15 minutes.

At subsequent study visits:

Once enrolled in the study, BP will be measured.

HR (beats/min) will be measured simultaneously during BP recording.

9.7.3 Blood Sample Collection

An appropriately trained and qualified personnel will perform the venipuncture procedure to collect the necessary blood samples as per standard phlebotomy techniques.

Blood samples will be collected for the analysis of:

- Serum levels of Immunoglobulin A (IgA), G (IgG), E (IgE) and M (IgM)
- Immune response biomarkers: CD14, CD163, CD40 (TNFRSF5), CRP (C-Reactive Protein), E-Selectin, Fas (TNFRSF6/Apo-1), Fas Ligand (TNFSF6), GCSF, ICAM-1 (CD54), IL-1 alpha (IL-1 F1), IL-1 beta (IL-1 F2), IL-1 R4 (ST2), IL-10, IL-12 p70, IL-13, IL18, IL-2, IL-2 R alpha, IL-4, IL-6, IL-8 (CXCL8), Lipocalin-2 (NGAL), MCP-1 (CCL2), MCP-2 (CCL8), MIF, MIP-1 alpha (CCL3), MIP-1 beta (CCL4), Osteopontin (SPP1), PAI-1, Platelet Factor 4 (CXCL4), Procalcitonin, RAGE, Resistin, Thrombomodulin, TNF alpha, TREM-1, Troponin I, uPAR, VCAM-1 (CD106), VEGF-A.

9.7.4 Stool Collection

Stool samples will be collected for study visit 2-Baseline-Day 0, and Visit 5- End of Study, Day 84 ± 2 days using the dispensed collection kits. Participants will be instructed on stool sample collection, storage, and transportation. Participants will be given a stool collection kit containing materials required to collect their stool sample. Stool samples should be collected within 4 calendar days of their next visit. The sample will be stored at room temperature after collection and transported to the clinic within 4 days of their clinic visit.

Stool samples will be used for a microbiome analysis. Microbiome analysis will be completed in n=80 participants. At the discretion of the Study sponsor microbiome analysis may be completed in additional completers to bolster study outcomes.

Genomic DNA will be extracted from the stool samples and stored at -80°C until PCR amplification. Upon completion of amplification amplicons will be stored at again at -80°C until further processing and time of analysis. Analysis sequence reads will be completed to infer exact sequence variants and taxonomy assigned including kingdom 'Eukaryota', order 'Chloroplasts' or the family 'Mitochondria'. Microbiota α-diversity analyses will be performed on unfiltered sequence variant counts tables.

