 - c. Immune response biomarkers: CD14, CD163, CD40 (TNFRSF5), CRP (C-Reactive Protein), E-Selectin, Fas (TNFRSF6/Apo-1), Fas Ligand (TNFSF6), GCSF, ICAM-1 (CD54), IL-1 alpha (IL-1 F1), IL-1 beta (IL-1 F2), IL-1 R4 (ST2), IL-10, IL-12 p70, IL-13, IL18, IL-2, IL-2 R alpha, IL-4, IL-6, IL-8 (CXCL8), Lipocalin-2 (NGAL), MCP-1 (CCL2), MCP-2 (CCL8), MIF, MIP-1 alpha (CCL3), MIP-1 beta (CCL4), Osteopontin (SPP1), PAI-1, Platelet Factor 4 (CXCL4), Procalcitonin, RAGE, Resistin, Thrombomodulin, TNF alpha, TREM-1, Troponin I, uPAR, VCAM-1 (CD106), VEGF-A.
 - d. Microbiome as assessed by 16s rRNA fecal microbiome analysis

Safety outcomes:

- 1. Incidence of post-emergent adverse events (AE)
- 2. Clinically relevant changes in vital signs (blood pressure (BP) and heart rate (HR)) after supplementation

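### Read literally, protocol section 9.7.4 lets eukaryotic, chloroplast and mitochondrial variants count in the alpha diversity of a 16S rRNA outcome

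*Protocol*

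**What the plan says.** Protocol section 5 lists, as secondary outcome 5d, "Microbiome as assessed by 16s rRNA fecal microbiome analysis", compared between arms as a change from baseline to day 84.

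The processing rules are in Protocol section 9.7.4 (Stool Collection). After DNA extraction and amplification, exact sequence variants are inferred and "taxonomy assigned including kingdom 'Eukaryota', order 'Chloroplasts' or the family 'Mitochondria". The next sentence reads: "Microbiota α-diversity analyses will be performed on unfiltered sequence variant counts tables". The same section sets the size of this analysis: "Microbiome analysis will be completed in n=80 participants", which the sponsor may extend.

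No sentence in section 9.7.4 removes any of the three named groups. Section 11.3 names methods for the symptom, medication, immunoglobulin and biomarker outcomes but none for the microbiome. Section 9.7.4 is therefore the only place in the protocol that says how outcome 5d is processed.

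**The concern.** The 16S rRNA gene is a marker for bacteria and archaea. Variants that are classified as eukaryotic, chloroplast or mitochondrial come from food plants, host cells or other eukaryotic material. They are by-products of the assay, not members of the community that it is meant to profile.

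The protocol names exactly these three groups, attaches the word *including* to them, and in the next sentence takes alpha diversity from a table described as unfiltered. An analyst who follows both sentences would let off-target variants count as diversity. Part of the result would then reflect what the child had eaten or how much host material was in the sample. Participants agree to keep their diet stable only as far as possible (section 7.1, item 6), so this part could differ between children and between the two visits for reasons unrelated to the product.

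This is not a complaint that laboratory or analysis detail is missing. The protocol states a rule, and its literal content works against the outcome that it serves.

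**Working it through.** The plan gives no figure to reproduce here. The check is a reading of the text, followed by an illustration of scale on assumed values.

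**Reading the text**

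1. Outcome (section 5, item 5d): a 16S rRNA profile of stool.
2. Taxonomy step (section 9.7.4): three off-target groups are named as included.
3. Alpha-diversity step (section 9.7.4): the input is the unfiltered variant count table.
4. Removal step: none is stated in section 9.7.4, and section 11.3 does not mention the microbiome.

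Taken at face value, steps 2 to 4 leave off-target variants in the table from which alpha diversity is computed.

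**Scale, on assumptions that the documents do not give**

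Assumed inputs:
- bacterial richness R of 100 to 200 variants
- bacterial Shannon index H_b of 3.0 to 4.0
- k = 1 to 10 off-target variants
- off-target share q of reads from 0.1% to 20%, spread evenly over the k variants

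*Observed richness* becomes R + k, so the relative increase is k/R. The smallest is 1/200 = 0.5% and the largest is 10/100 = 10%. Richness can only rise.

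*Shannon index* becomes

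H = (1 - q) × H_b + h(q) + q × ln(k), with h(q) = -q ln q - (1 - q) ln(1 - q).

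Two worked cases:
- H_b = 3.0, q = 0.05, k = 10: 0.95 × 3.0 + 0.199 + 0.05 × 2.303 = 2.850 + 0.199 + 0.115 = 3.164, a shift of +0.164.
- H_b = 4.0, q = 0.20, k = 1: 0.80 × 4.0 + 0.500 + 0 = 3.700, a shift of -0.300.

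Range of the shift over the values of H_b and k that were tried (H_b = 3.0, 3.5, 4.0; k = 1, 5, 10):

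| Off-target share q | Lowest shift | Highest shift |
|---|---|---|
| 0.1% | +0.004 | +0.007 |
| 5% | -0.001 | +0.164 |
| 20% | -0.300 | +0.361 |

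The effect is negligible when off-target reads are rare. It becomes visible, with a sign that depends on the sample, when they are common.

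**What reaches the comparison between arms**

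Outcome 5d is a difference in change. If a child carries the same number k of off-target variants at both visits, the change in richness is (R_84 + k) - (R_0 + k) = R_84 - R_0, and k cancels. Only visit-to-visit variation in k enters the change. Allocation is randomised and blinded, so that variation is expected in both arms and shows as extra variance.

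**The case against.** The strongest reply is that assigning a label is not the same as keeping the read. Off-target variants have to be classified before they can be removed, so the taxonomy sentence is compatible with later removal. Its grammar, with *including* followed by a list joined by *or*, also suggests an exclusion clause that was garbled in editing. *Unfiltered* is undefined and may mean only that no prevalence or abundance filter is applied. Pipeline detail of this kind is often left to an analysis plan or a laboratory plan, and neither is at hand.

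Much of this stands. It cannot be said that off-target reads will be counted, only that the text, followed literally, would count them. It does not remove the point. If exclusion was meant, the protocol says the opposite, and the following sentence reinforces the wrong reading. Nothing elsewhere in the protocol corrects it, and a later plan that excluded these taxa would have to depart from the wording.

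A reader might infer two stronger things that the protocol does not support:

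- *That off-target reads distort every relative abundance by inflating the denominator.* The protocol describes no relative-abundance analysis. Section 9.7.4 applies the word unfiltered to alpha diversity alone, and section 11.3 names no microbiome analysis.
- *That the comparison between arms is biased.* Arms are randomised and blinded, and section 9.9 keeps those who analyse the samples unaware of the product received. Diet and host reads are expected to affect both arms alike.

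**Conclusion.** The point holds as a minor correction to wording that, taken literally, gives a worse analysis. The sentence on taxonomy and the sentence on unfiltered tables together admit off-target variants into the alpha diversity of a 16S outcome.

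The size cannot be derived from the documents and may be small. The ranges in the working rest wholly on assumed richness, Shannon index, variant count and read share. That the community of interest is bacterial is inferred from the 16S marker; the protocol itself says only microbiota. The expected harm is added noise in secondary outcome 5d. No primary outcome and no sample-size figure depends on it.

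**What to change.** Reword the two sentences in section 9.7.4 to say that:

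1. after taxonomy is assigned, variants classified as Eukaryota, Chloroplast or Mitochondria are removed before alpha diversity and any other microbiome analysis; and
2. alpha diversity is then computed on the remaining counts, where unfiltered means that no prevalence or abundance filter is applied after that removal.

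If keeping these variants was in fact intended, the section should say so and give the reason.

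The cost is a sentence or two of text, documented as an amendment under sections 9.11 and 11.5. It needs no new samples and no extra laboratory work, because removal is done on the variant table. It should be settled before the sequence data are analysed.

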9.7.5 Saliva Sample Collection

Participants will be instructed on the collection of salivary samples for the analysis of IgA levels by study staff. Samples will be collected using saliva collection kits as per manufacturer's instructions and frozen immediately following sample collection at Visit 2- baseline (Day 0) and Visit 5-Day 84 ± 2 days. Saliva sample should be collected in the morning on the day of or day preceding their in-clinic visit.

9.7.6 Study Diary

Participant caregiver's will be instructed to complete the study diary daily. Questions pertaining to IP compliance, lifestyle habits, concomitant medications (inclusive of OTC medications and vaccinations), tracking cold/flu and GITI symptoms (see Sections 9.7.7, 9.7.8, and 9.7.9 below), missed school days, and any adverse events and symptoms throughout the study will be included. Each day, caregivers will ask if their child has any of the symptoms listed in the CARIFS, Additional Respiratory Tract Symptoms or GITI Symptom Questionnaires (Sections 16.1, 16.2, and 16.3). Caregivers will report all symptoms in the study diary daily using the CARIFS, Additional Respiratory Tract Symptoms, and GITI Symptoms Questionnaires.

9.7.7 Canadian Acute Respiratory Illness Flu Scale (CARIFS)

The Canadian Acute Respiratory Illness Flu Scales (CARIFS) is an 18-item questionnaire for children that assesses respiratory illness severity across three domains: symptoms, function and parental impact (**Section 16.2**). Each item is answered on a 4-point scale (no problem = 0, minor problem = 1, moderate problem = 2, major problem = 3), with a higher score denoting a more severe illness (20,21). Participants will complete the CARIFS daily throughout run-in and the study period as part of their study diary. As referenced by *Lazou Ahren et al.* (2020) and *Singh et al.* (2024), incidence, duration, and severity of cold and flu will be defined as the following (21,22):

- *Incidence* will be defined as two or more consecutive days with scores above zero (no problem) in at least two symptoms (headache, sore throat, muscle aches or pain, fever, cough, nasal congestion or runny nose, and vomiting; items 10–16) listed on the CARIFS (21).
- *Duration* will be defined as the length of time from an onset of an incidence (defined above) until the last day with symptoms followed by two days with a 0 score
- Severity will be calculated using two methods. 1) The mean total severity score per day of the individual items per incidence of cold or flu symptoms, and 2) area under the curve (AUC) of daily total symptom scores.

9.7.8 Gastrointestinal Tract Infection (GITI) Symptoms Questionnaire

Gastrointestinal tract infection (GITI) symptoms will be assessed by completion of the Gastrointestinal tract infection symptoms questionnaire. These questions will completed daily throughout run-in and the study period as part of their study diary. See **Section 16.1** for the questions in this questionnaire.

The GITI symptom questionnaire will comprise the record of the incidence, duration, and severity of individual GITI symptoms. Each item is answered on a 4-point scale (no problem = 0, minor problem = 1, moderate problem = 2, major problem = 3), with a higher score denoting a more severe illness. Participants

will complete the GITI symptom questionnaire daily throughout run-in and the study period as part of their study diary.

Incidence, duration, and severity of GITI symptom will be defined as the following:

- Incidence of a symptom will be defined as the first day with a score of greater than 0
- *Duration of a symptom* will be defined as the length of time from the onset of an incidence (defined above) until the last day the symptom is reported followed by a day with a score of 0
- Severity of a symptom will be calculated using two methods: 1) The mean of the specific symptom scores during the investigational period, and 2) the area under the curve (AUC) of individual symptom scores during the investigational period.

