5 STUDY OBJECTIVES

The objective of this study is to investigate the safety and efficacy of *Bacillus coagulans* SNZ 1969 on the incidence rate, duration, and severity of acute upper respiratory tract infections (URTI) and gastrointestinal tract infection (GITI) symptoms in healthy school-aged children.

Primary outcomes:

- 1. The difference in incidence, duration, and severity (area-under-the-curve (AUC)) of URTI as assessed by the Canadian Acute Respiratory Illness and Flu Scale (CARIFS) from baseline to day 84 between *Bacillus coagulans* SNZ 1969 and placebo
- 2. The difference in incidence, duration, and severity (area-under-the-curve (AUC)) of Additional Respiratory Tract Symptoms as assessed by Additional Respiratory Tract Symptoms questionnare from baseline to day 84 between *Bacillus coagulans* SNZ 1969 and placebo
- 3. The difference in incidence, duration, and severity (AUC) of GITI symptoms as assessed by the GITI Symptoms Questionnaire from baseline to day 84 between *Bacillus coagulans* SNZ 1969 and placebo

Secondary outcomes:

[figure not shown]
- 1. The difference in incidence, duration, and severity (AUC) of URTI as assessed by the CARIFS from baseline to days 28 and 56 between *B coagulans* SNZ 1969 and placebo
- 2. The difference in incidence, duration, and severity (AUC) of Additional Respiratory tract symptoms as assessed by Additional Respiratory Tract Symptoms questionnare from baseline to days 28 and 56 between *B coagulans* SNZ 1969 and placebo
- 3. The difference in incidence, duration, and severity (AUC) of GITI symptoms as assessed by the GITI Symptoms Questionnaire from baseline to days 28 and 56 between *B. coagulans* SNZ 1969 and placebo
- 4. The difference between *B. coagulans* SNZ 1969 and placebo from baseline to days 28, 56, and 84 on:
 - a. Severity of cold/flu and GITI symptoms as assessed by total and individual daily symptom scores
 - b. Number of missed school days
 - c. Number of well days, related to the absence of cold/flu and GITI symptoms
 - d. Use of prescription and non-prescription cold/flu medications to treat cold or flu symptoms
 - e. Total days of illness
- 5. The difference in change between B. coagulans SNZ 1969 and placebo from baseline to day 84 on:
 - a. Saliva secretory immunoglobulin A (sIgA) concentrations
 - b. Serum levels of Immunoglobulin A (IgA), G (IgG), E (IgE) and M (IgM)

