9.7.9 Additional Respiratory Tract Symptoms Questionnaire

Additional respiratory tract symptoms will be collected and administered in the same format as the CARIFS. This questionnaire will comprise the record of the incidence, duration, and severity of the individual symptoms. Each item is answered on a 4-point scale (no problem = 0, minor problem = 1, moderate problem = 2, major problem = 3), with a higher score denoting a more severe illness. Participants will complete the questionnaire daily throughout run-in and the study period as part of their study diary.

Additional Symptom data to be collected for the following respiratory symptoms: yellow mucus, bloody mucus, crystalline mucus, itchy nose, itchy throat, red eyes, hoarseness, and sneezing (Section 16.3).

Incidence, duration, and severity of symptoms will be defined as the following:

- Incidence of a symptom will be defined as the first day with a score of greater than 0
- Duration of a symptom will be defined as the length of time from the onset of an incidence (defined above) until the last day the symptom is reported followed by a day with a score of 0
- Severity of a symptom will be calculated using two methods: 1) The mean of the specific symptom scores during the investigational period, and 2) the area under the curve (AUC) of individual symptom scores during the investigational period.

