11 STATISTICAL EVALUATION

11.1 Determination of Sample Size

Assuming placebo participants would experience 1.43 episodes of URTIs and 7.42 duration days of URTI symptoms during 84 days of follow up (22), a sample size of 100 participants (50 participants per arm) has a power of 80% to detect a rate of \leq 0.76 for the number of episodes of URTIs and \leq 5.80 for the duration days of URTI symptoms in the Bacillus coagulans SNZ 1969 group using Poisson regression model.

In addition, a sample size of 100 participants could detect an effect size ≥ 0.63 in the AUC of GITI symptom scores and in the AUC of the Additional Respiratory Tract Symptoms questionnaire, and a difference of ≥27.8 score.day in the mean of AUC of CARIFS daily total symptom scores between Bacillus coagulans SNZ 1969 and placebo groups assuming standard deviations equal to 52.96 and 32.85 score.day for Bacillus coagulans SNZ 1969 and placebo groups (22), respectively, using two-sample t-test with 80% power, 2-sided 5% significance level, and 20% dropout rate.

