11.3 Statistical Analysis Plan

For both count and continuous primary and secondary outcomes, summary statistics including number of participants, mean, median, standard deviation, first quartile, third quartile, minimum, and maximum will be obtained for each available time interval and for each group. For categorical outcomes, frequencies and percentages will be presented.

The difference in the number of incidences of URTI, duration days of URTI, missed school days, well days, illness days between Bacillus coagulans SNZ 1969 and Placebo groups will be assessed by computing the rate ratio with 95% confidence interval using a generalized linear model with log link function (Poisson or negative binomial regression model).

The difference in the number of incidences of Additional Respiratory Symptoms and the duration days of Additional Respiratory Symptoms between Bacillus coagulans SNZ 1969 and Placebo groups will be assessed by computing the rate ratio with 95% confidence interval using a generalized linear model with log link function (Poisson or negative binomial regression model).

The difference in the number of incidences of GITI symptoms, duration days of GITI symptoms, missed school days, well days, illness days between Bacillus coagulans SNZ 1969 and Placebo groups will be assessed by computing the rate ratio with 95% confidence interval using a generalized linear model with log link function (Poisson or negative binomial regression model).

The difference in the AUC for daily total CARIFS scores, the mean total severity scores of URTI symptoms, the AUC for daily total Additional Respiratory Tract Symptoms questionnaire scores, the AUC of GITI symptom scores, and mean of GITI symptom scores between Bacillus coagulans SNZ 1969 and Placebo groups will be assessed by two-sample t-test if the outcome is normally distributed and Wilcoxon's rank sum test if the outcome is not normally distributed. Normality assumption will be assessed using quantile-quantile (Q-Q) plots.

Fisher's exact test will be used to assess the difference of proportion of participants who used prescription and non-prescription cold/flu medications to treat URTI/GITI symptoms between Bacillus coagulans SNZ 1969 and Placebo. 95% confidence interval of odds ratio will be calculated.

Differences between groups for sIgA, IgA, IgG, IgE, IgM, and immune response biomarkers at day 84 will be assessed by ANCOVA model adjusting for baseline values.

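### GITI and Additional Respiratory symptom incidence: the rule leaves open whether recurrences count, and if they do, the count is not monotone in symptom burden

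*Protocol*

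**What the plan says.** Section 5 lists three primary outcomes, each combining incidence, duration and severity. The third reads: "The difference in incidence, duration, and severity (AUC) of GITI symptoms as assessed by the GITI Symptoms Questionnaire from baseline to day 84 between" the two arms. The second has the same structure for Additional Respiratory Tract Symptoms.

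For both questionnaires the unit is the individual symptom. Sections 9.7.8 and 9.7.9 use the same onset rule, "Incidence of a symptom will be defined as the first day with a score of greater than 0", and the same end of duration, "until the last day the symptom is reported followed by a day with a score of 0". Neither section gives a minimum gap before a symptom can be counted again, a statement on recurrence, or a use for the diary kept during the 14-day run-in (9.2).

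Section 11.3 analyses these as counts by Poisson or negative binomial regression: "The difference in the number of incidences of GITI symptoms, duration days of GITI symptoms" and, separately, "The difference in the number of incidences of Additional Respiratory Symptoms and the duration days of Additional Respiratory Symptoms".

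For CARIFS, Section 9.7.7 works differently. An incidence needs "two or more consecutive days with scores above zero (no problem) in at least two symptoms", and its duration runs "until the last day with symptoms followed by two days with a 0 score".

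**The concern.** A primary measure should have one derivation from the diary and should move in a known direction when children do better. This one has two possible derivations.

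- If each return of a symptom after a zero day counts, the result is a number of interruptions as much as a number of occurrences. A child whose near-daily symptom becomes intermittent adds incidences while having fewer symptomatic days.
- If only the first day in the study counts, the result per symptom is yes or no. A child with one bad day and a child with twelve separate bad days score the same.

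Two analysts could therefore obtain different primary results from the same diaries. Under the repeat-count derivation, a rate ratio above 1 need not mean more illness. In addition, as the rule is written, a symptom present throughout run-in and still present on Day 1 enters the count as a new event, although it began before any product was taken.

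**Working it through.** **The plan's own figures.** The protocol gives no assumed rate or power for GITI or Additional Respiratory incidence. Section 11.1 rests on URTI: "Assuming placebo participants would experience 1.43 episodes of URTIs and 7.42 duration days of URTI symptoms during 84 days of follow up". With 20% dropout, 50 × 0.8 = 40 per arm. For Poisson rates, SE of the log rate ratio = √(1/(n·r₁) + 1/(n·r₂)).

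- Episodes, 1.43 against 0.76: SE = √(1/57.2 + 1/30.4) = 0.224; ln(1.43/0.76) = 0.632; power 80.4%.
- Duration days, 7.42 against 5.80: SE = √(1/296.8 + 1/232) = 0.0876; ln(7.42/5.80) = 0.246; power 80.3%.
- Effect size 0.63 for the GITI and Additional Respiratory AUCs: 79.5% by the t-test. CARIFS AUC difference of 27.8: 79.6%.

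These reproduce the stated 80%, and none of them uses the incidence definition at issue.

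**Fixed patterns, one symptom, score 1 when present, 84 days.**

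| Pattern | Symptom-days | Mean score | Incidences, recounted after one zero day | Incidences, first day only | Incidences, recounted after two zero days |
|---|---|---|---|---|---|
| Every day | 84 | 1.0 | 1 | 1 | 1 |
| Alternate days | 42 | 0.5 | 42 | 1 | 1 |
| One day in seven | 12 | 0.14 | 12 | 1 | 12 |
| One five-day spell | 5 | 0.06 | 1 | 1 | 1 |

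Strict alternation is the maximum possible, 84/2 = 42. The figures are for one symptom; the appendices list 13 GITI items and 8 Additional Respiratory items. On the first-day-only reading, a total over items cannot exceed 13 or 8 per child.

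**Shape of the count when restarts count.** Assume a symptom is present on each day independently with probability p. Day 1 contributes p, and each of the other 83 days contributes p(1−p), that is, present today and absent yesterday. The expected count is p + 83p(1−p).

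| p | Expected incidences | Expected symptom-days (84p) |
|---|---|---|
| 0.10 | 7.6 | 8.4 |
| 0.25 | 15.8 | 21.0 |
| 0.50 | 21.3 | 42.0 |
| 0.75 | 16.3 | 63.0 |
| 0.90 | 8.4 | 75.6 |
| 1.00 | 1.0 | 84.0 |

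Setting the derivative 1 + 83(1−2p) to zero gives p = 84/166 = 0.51. Below that the count moves with burden; above it the count moves against burden.

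**Does the CARIFS rule avoid this?** Not fully. Two qualifying symptoms for two days, then two clear days, repeated, gives 84/4 = 21 incidences and 42 symptomatic days under 9.7.7. Symptoms on every day give 1 incidence and 84 days.

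**What a two-zero-day gap does for a single symptom.** Alternate days fall from 42 to 1. The largest possible count falls from 42 to 84/3 = 28 (one day on, two off). With independent days, and the days before Day 1 following the same p, the expected count is 84·p(1−p)². This peaks at p = 1/3 with 84 × 4/27 = 12.4, against a peak of about 21.3 now. The gap rule lowers the count and removes day-to-day flicker, but it does not make the count monotone.

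**The case against.** The strongest reply has four parts.

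**Healthy children.** Enrolment excludes asthma, severe environmental allergies and relevant gastrointestinal and respiratory disorders, as the investigator judges. Nothing in the protocol suggests that symptoms on more than half of days will be common, and below that level the count moves the right way. This stands. It rules out the inference that the measure runs backwards in general: the reversal is confined to persistent symptoms, and how many children have them is not known from the document.

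**Other primary measures.** Duration days and severity order the daily and alternate-day child correctly (84 against 42 days; mean score 1.0 against 0.5). This also stands, with one gap: the daily child never has the zero day that closes a duration. It limits the damage, but incidence is still a named part of two primary outcomes and has its own rate ratio.

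**Different constructs.** CARIFS defines illness episodes, while the other two questionnaires record individual symptoms. A reader might infer that one day of minor flatulence is being called an infection, or that all three domains must share the two-symptom rule. The documents support neither. The outcome is worded as GITI symptoms, and a two-symptom rule would drop, for example, several days of isolated diarrhoea.

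**Left to the SAP.** Recurrence and merging rules are often set there, and the SAP is not shown. That would settle an omission. Here the protocol itself fixes onset at the first day above zero, and a recurrence rule written later would have to reinterpret that wording.

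**Conclusion.** The point holds as a defect in the definition of a primary measure. The wording admits two derivations. With repeat counting, the number of incidences is not monotone in burden and turns at about half of days (p = 0.51 for independent days), with 1 against 42 as the extreme contrast for one symptom. With first-day counting, each symptom is capped at one and recurrence is ignored, which fits poorly with a Poisson or negative binomial rate ratio. Repeat counting is the more natural reading, because 11.3 models a number of incidences and duration is measured from the onset of an incidence, but the protocol does not state it. The failure to screen out symptoms ongoing from run-in applies under both.

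The turning point rests on independence between days. The 1 against 42 contrast is exact arithmetic but a constructed pattern. The size of any effect on the trial's rate ratio cannot be given, because the protocol contains no data on how often these symptoms occur or persist.

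A reader might also infer that Section 9.7.7 is free of the problem, or that the sample size is undermined. Neither follows: 9.7.7 can give 21 against 1, and no stated power figure uses GITI or Additional Respiratory incidence.

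**What to change.** Amend 9.7.8 and 9.7.9, before unblinding, as follows:

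1. Keep incidence at the level of the individual symptom, and state that recurrences count.
2. State that a new incidence of a symptom requires at least two consecutive zero days since its last reported day, which is the closing rule already used in 9.7.7.
3. Count only onsets on or after Day 1 that are not ongoing from run-in, judged from the run-in diary by the same two-day gap.
4. Read the incidence rate ratio alongside total symptom-days, since any episode count can rise when a continuous symptom becomes intermittent. The existing duration-days measure serves for this if it stays a count of days with a score above 0. If the two-day gap were carried into duration as elapsed time, the alternate-day child would score 83 days (Day 1 to Day 83) instead of 42. State also how a symptom still present at the end of the diary is closed.

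A second symptom or a two-day minimum for GITI is optional and not part of this change.

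The cost is rewording two sections and deriving the counts from the same diary, with no new data collection. Fewer incidences will be counted, and relapses after a one-day gap will be merged. The sample-size figures in 11.1 stay as they are.
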